1.3 Synopsis

Title:	Phase II Trial to assess the Efficacy of Low Radiation Dose of 20 Gy for the Treatment of Marginal Zone Lymphoma or Follicular Lymphoma Stage I-II localized in the Stomach or the Duodenum
Short Title:	ISRT 20 Gy in Localized Indolent G astric or D uodenal L ymphoma
Acronym	GDL-ISRT 20 Gy
Protocol version identifier:	01, 23.08.2020
Register-No.	NCT04097067 (ClinicalTrials.gov)
Lead Investigators:	[name]. med. [name]/ Dr. med. [name]
Indication/ Medical condition:	Primary indolent (marginal zone or follicular) gastric or duodenal lymphoma
Study Design:	Prospective single-arm multicenter study
Active substance/ Medicinal product	None
Intervention(s):	Involved Site RadioTherapy (ISRT) with 20 Gy
Treatment plan	-Study enrollment, blood draw for biomarker-analysis (at baseline visit/ after 4 Gy/ after 10 Gy / after 20 Gy RT/ at 3 and 6 months after RT) -CT-based planning of RT - ISRT with IMRT (oder 3D-CRT)/ IGRT , daily 2 Gy ad 20 Gy
Objectives:	-Prove the effectiveness of 20 Gy and non-inferiority to 30 Gy with respect to response rate. -Recording of survival rates, quality of life (QoL), radiogenic toxicities and inflammation relevant molecules. -Primary Objective: Response rate 6 months after end of treatment, 4 categories according to GELA-criteria: CR (complete remission) = CR or pMRD (probable minimal residual disease), PR (partial remission) = rRD (responding residual disease), NC (no change), PD (progressive disease) -Secondary Objectives: QoL according to EORTC (QLQ C30 and STO22). EFS=Event-free survival (time to any failure or death from any cause, all patients), PFS=Progression-free survival (time to progression of lymphoma or death from any cause, patients in PR or SD), RFS=Recurrence-free survival (time to recurrence of lymphoma or death from any cause, patients in CR), LSS=Lymphoma-specific survival (time to death related to lymphoma or associated with the treatment, all patients), OS=Overall survival

	
(time to death from any cause, all patients). Level of cytokines IL-1β, IL-4, IL-8, TNFα and other inflammation relevant molecules Syndecan1, MMP-2 and S100 proteins. Acute toxicities during treatment according to NCI-CTC, chronic toxicities according to NCI-CTC/ LENT-SOMA.
 
Monitoring of Adverse Events (AEs) and Serious Adverse Events (SAEs)
 
-Assessment of safety: Monitoring of Adverse Events (AEs) and Serious Adverse Events (SAEs)

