3.2.2 Secondary Endpoints

-**Quality of life** (QoL) according to EORTC (QLQ C30 and STO22), at baseline visit/ after 20 Gy (=last day of RT)/ 6 months after end of RT.

-**EFS**=Event-free survival (time from beginning of RT to any failure or death from any cause, all patients). Follow-up over 2 years after end of RT.

-**PFS**=Progression-free survival (time from beginning of RT to progression of lymphoma or death from any cause, patients in PR or SD). Follow-up over 2 years after end of RT.

-**RFS**=Recurrence-free survival (time from beginning of RT to recurrence of lymphoma or death from any cause, patients in CR). Follow-up over 2 years after end of RT.

-**LSS**=Lymphoma-specific survival (time from beginning of RT to death related to lymphoma or associated with the treatment, all patients). Follow-up over 2 years after end of RT.

-**OS**=Overall survival (time from beginning of RT to death from any cause, all patients). Follow-up over 2 years after end of RT.

-Level of **cytokines IL-1 β , IL-4, IL-8, TNF α** and other inflammation relevant molecules: **Syndecan1 and MMP-2** and **S100 proteins** at baseline visit/ after 4 Gy/ after 10 Gy/ after 20 Gy on last day of RT/ at 3 and 6 months after end of RT.

-**Acute toxicities** during treatment, 6 weeks after end of RT, according to NCI-CTC

-**Chronic toxicities** from 3 months up to 2 years after end of RT, according to NCI-CTC/ LENT-SOMA.

-Incidence of **Adverse Events** (AEs) and **Serious Adverse Events** (SAEs), continuously.

4 Study Design

-Single-arm, prospective, open label, interventional, multicenter study.

-Historic data from irradiated patients with indolent gastrointestinal lymphomas serves as a basis for the intended response rate.

-Participation of further international sites with expertise in radiation treatment of gastrointestinal lymphomas after approval of their Ethics Committee/ IRB.

-Number of 79 patients need to be analyzed.

-Justification for 'single-arm design' and for 'non-inferiority limit': the low prevalence of the disease, the limited risk of the study design (because of the option of renewed RT in case of persisting disease) and the benefit in terms of lower risk of adverse reactions due to the lower RT dose of 20 Gy in comparison to standard dose of 30 Gy.

5 Study Sites and Study Population

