8.3 Follow-up examinations

8.3.1 FU-1

The first follow-up visit after RT takes place 6 weeks after the termination of RT \pm 5 days and should include the following examinations:

- Anamnesis
- Clinical examination: ECOG, weight, blood pressure
- Acute radiogenic reactions must be documented (see Appendix 16.5 Adverse Reactions according to CTCAE)

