8.3.2 FU-2 – FU-6

The further exams take place quarterly in the first year after treatment (FU-2 – FU-5), afterwards an annual visit is scheduled (FU-6).

FU-2:	3 months after end of RT ± 3 weeks
FU-3:	6 months after end of RT ± 3 weeks
FU-4:	9 months after end of RT ± 3 weeks
FU-5:	12 months (1 year) after end of RT ± 3 weeks
FU-6:	24 months (2 years) after end of RT ± 3 weeks

The FU-2 and FU-3 visits include blood draw!

At all follow-up visits (FU-2 – FU-6) chronic radiogenic reactions must be documented (see Appendix 16.6 Adverse Reactions according to LENT SOMA).

Each follow-up visit consists of the following examinations:

- Anamnesis
- Clinical examination: ECOG, weight, blood pressure
(at FU-1/-2/-3/-5/-6)
- Quality of life assessment with QLQ-C30 and STO-22 (at FU-1/-2/-3)
- Endoscopy/ Endosonography (+ biopsies) (at FU-2/-3/-5/-6)
- CT-imaging (at FU-3/-5/-6)
- **Blood draw (at FU-2/-3):**
 - o –Routine: small blood count, LDH, GOT, GPT, alcalic phosphatase, γ-GT, bilirubin, creatinine.
 - o –**Research program (analyses at the University of Muenster!):**
Two 7.5 - 9 ml serum monovettes.
Centrifugation, freezing and storage see 3.1.3 and Appendix 16.7 (SOP BLOOD SAMPLES for RESEARCH PROGRAM)
Transmission of frozen blood samples to Radiobiology lab, Muenster at the cost of Dept. of Radiation Oncology, University Hospital Muenster
- Chronic radiogenic reactions must be documented (see Appendix 16.6 Adverse Reactions according to LENT SOMA)

The FU-6 is the study termination visit and ends the study regularly.

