ALSO CONSIDER: Adult Respiratory Distress Syndrome (ARDS); Cough; Dyspnea (shortness of breath); Hypoxia; Infection (documented clinically or microbiologically) with Grade 3 or 4 neutrophils (ANC <1.0 x 10 ⁹ /L) – Select ; Infection with normal ANC or Grade 1 or 2 neutrophils – Select ; Infection with unknown ANC – Select ; Pneumonitis/pulmonary infiltrates; Pulmonary fibrosis (radiographic changes).						
Pneumothorax	Pneumothorax	Asymptomatic, radiographic findings only	Symptomatic; intervention indicated (e.g., hospitalization for observation, tube placement without sclerosis)	Sclerosis and/or operative intervention indicated	Life-threatening, causing hemodynamic instability (e.g., tension pneumothorax); ventilatory support indicated	Death
PULMONARY/UPPER RESPIRATORY						
Grade						
Adverse Event	Short Name	1	2	3	4	5

Pulmonary fibrosis (radiographic changes)	Pulmonary fibrosis	Minimal radiographic findings (or patchy or bi-basilar changes) with estimated radiographic proportion of total lung volume that is fibrotic of <25%	Patchy or bi-basilar changes with estimated radiographic proportion of total lung volume that is fibrotic of 25 – <50%	Dense or widespread infiltrates/consolidation with estimated radiographic proportion of total lung volume that is fibrotic of 50 – <75%	Estimated radiographic proportion of total lung volume that is fibrotic is ≥75%; honeycombing	Death
---	--------------------	--	--	---	---	-------

REMARK: Fibrosis is usually a “late effect” seen >3 months after radiation or combined modality therapy (including surgery). It is thought to represent scar/fibrotic lung tissue. It may be difficult to distinguish from pneumonitis that is generally seen within 3 months of radiation or combined modality therapy.
ALSO CONSIDER: Adult Respiratory Distress Syndrome (ARDS); Cough; Dyspnea (shortness of breath); Hypoxia; Infection (documented clinically or microbiologically) with Grade 3 or 4 neutrophils (ANC <1.0 x 10⁹/L) – *Select*; Infection with normal ANC or Grade 1 or 2 neutrophils – *Select*; Infection with unknown ANC – *Select*.

NAVIGATION NOTE: Recurrent laryngeal nerve dysfunction is graded as Laryngeal nerve dysfunction in the NEUROLOGY CATEGORY.

Vital capacity	Vital capacity	90 – 75% of predicted value	<75 – 50% of predicted value	<50 – 25% of predicted value	<25% of predicted value	Death

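### The acute and chronic toxicity windows in 3.2.2 do not meet, so a reaction confined to the interval between FU-1 and FU-2 belongs to neither endpoint; the synopsis and 8.3.2 also depart from 3.2.2

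*Protocol*

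**What the plan says.** Section 3.2.2 lists three safety endpoints that bear on this point:

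- acute toxicity, "during treatment, 6 weeks after end of RT, according to NCI-CTC";
- chronic toxicity, "from 3 months up to 2 years after end of RT, according to NCI-CTC/ LENT-SOMA";
- incidence of adverse events and serious adverse events ("SAEs), continuously").

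The synopsis (1.3) gives the first two as "Acute toxicities during treatment according to NCI-CTC, chronic toxicities according to NCI-CTC/ LENT-SOMA". It does not mention the 6-week time point.

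On data collection, 8.3.1 states that "The first follow-up visit after RT takes place 6 weeks after the termination of RT", with a tolerance of 5 days either way, and that at this visit "Acute radiogenic reactions must be documented (see Appendix 16.5 Adverse Reactions according to CTCAE"). Section 8.3.2 sets FU-2 at 3 months with a tolerance of 3 weeks and says that at FU-2 to FU-6 "chronic radiogenic reactions must be documented (see Appendix 16.6 Adverse Reactions according to LENT SOMA"). The schedule table in section 8 agrees: its row for acute reactions ends at FU-1 and its row for chronic reactions begins at FU-2. Section 9.1 ties acute toxicity to CTCAE and chronic toxicity to LENT SOMA.

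**The concern.** Two endpoints that together should describe radiation toxicity over the two years after RT have a hole between them. Followed as written, the acute rate stops at 6 weeks and the chronic rate starts at 3 months. The acute endpoint also has two definitions, so the same data could yield two acute rates, depending on whether the synopsis or 3.2.2 is used.

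This matters because low toxicity is the patient benefit claimed in 2.2, and section 4 uses the expected lower risk of adverse reactions to justify the single-arm design and the non-inferiority limit. With no control arm, the toxicity rates can only be set against outside data, and such a comparison needs a window and a scale that are unambiguous.

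**Working it through.** The plan gives no figure on this point that could be reproduced. The check compares definitions and does simple date arithmetic.

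**1. Length of the unassigned interval.** Inputs: FU-1 at 6 weeks = 42 days, tolerance 5 days (8.3.1); FU-2 at 3 months, tolerance 3 weeks = 21 days (8.3.2). One month is taken as 365.25/12 = 30.44 days, so 3 months = 91.3 days.

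- Nominal: 91.3 − 42 = 49.3, about 49 days.
- Shortest (FU-1 late, FU-2 early): (91.3 − 21) − (42 + 5) = 70.3 − 47 = 23.3, about 23 days.
- Longest (FU-1 early, FU-2 late): (91.3 + 21) − (42 − 5) = 112.3 − 37 = 75.3, about 75 days.

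**2. Which reactions fall out.**

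| Course of the reaction | Endpoint under 3.2.2 |
|---|---|
| Starts during RT or by FU-1 and is recorded there | acute |
| Starts after FU-1 and is still present at FU-2 | recorded at FU-2 as chronic |
| Starts after FU-1 and resolves before FU-2 | neither |

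Only the third row is affected: the whole course has to fit between the two visits. The documents say nothing about how many reactions do so, so no rate of omission can be derived.

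**3. Definition of acute toxicity.** The synopsis covers treatment only. Section 3.2.2, the schedule table and 8.3.1 all include the 6-week visit. Three places agree and the synopsis is the outlier.

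**4. Scale after FU-1.** For chronic toxicity 3.2.2 names NCI-CTC and LENT-SOMA, while 8.3.2 and 9.1 point to LENT SOMA alone. So no scheduled visit after FU-1 is told to grade on CTCAE. The two scales are not interchangeable: CTCAE grades single events from 1 to 5 (9.1, Appendix E), whereas LENT SOMA grades parameters from 1 to 4 and averages them within an organ (Appendix F).

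**5. What still captures an event in the interval.** Section 9.2 requires adverse reactions during follow-up to be graded on the acute and chronic toxicity forms and sent within 7 days. By the definition in 9.1, an adverse event counts whether or not it is related to RT, and AE/SAE incidence has no time gap. The event therefore reaches the database and one secondary endpoint. What is missing is a rule saying which toxicity form, and hence which scale and which toxicity rate, takes a reaction arising in, say, week 9.

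**The case against.** The strongest reply is that nothing is lost. AE/SAE incidence is a continuous endpoint in the same list. Reporting under 9.2 is mandatory, graded and not tied to visit days, and 8.1 has patients encouraged to report conditions during and after RT. FU-1 and FU-2 are consecutive visits, so no planned assessment is skipped, and the 49 days are visit spacing rather than a share of toxicity missed. The operative acute definition is clear from the schedule and 8.3.1. Everything beyond the primary analysis is exploratory (11.3).

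Most of this stands, and it rules out several stronger readings that a reader might draw:

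- *Toxicity as a whole is under-counted.* The documents do not support this, because 9.2 and the continuous endpoint pick the events up.
- *Radiation pneumonitis falls in the gap.* Appendix E speaks of "pneumonitis that is generally seen within 3 months of radiation or combined modality therapy". That period starts at RT; it overlaps the interval but does not place pneumonitis inside it.
- *FU-1 sees only a fraction of post-treatment reactions.* With onset uniform over 42 days and durations of 7 to 21 days, one would get 7/42 = 17% to 21/42 = 50% present at the visit. Neither the onset pattern nor the durations are in the protocol, and 8.3.1 does not restrict recording to what is present that day. Whether the form asks for the worst grade since the last visit may properly be settled in the CRF or SAP.

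What the reply does not remove is the definitional gap. All-cause AE incidence is a different quantity from a radiogenic toxicity rate. Section 9.2 does not say whether a reaction in the interval goes on the acute or the chronic form, so many centers may classify it differently. Neither definition in 3.2.2 includes it.

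**Conclusion.** The point holds as a defect in endpoint definition. By the wording of 3.2.2, a reaction confined to the time between FU-1 and FU-2 (about 49 days nominally, 23 to 75 days with the tolerances) belongs to neither toxicity endpoint, although it remains reportable under 9.2 and counts in AE/SAE incidence. The synopsis conflicts with 3.2.2, the schedule and 8.3.1 on what acute means, and 8.3.2 does not match the scales that 3.2.2 names for chronic toxicity. The day counts rest only on the stated visit times and a month of 30.44 days. The effect on the reported toxicity rates cannot be computed from the protocol, and an overall loss of toxicity data should not be inferred. The primary response analysis is untouched. The repair is worth making because it is cheap and the toxicity rates carry part of the case for 20 Gy.

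**What to change.** - Use one definition in 1.3 and 3.2.2, with windows that meet. Acute: worst CTCAE grade of any reaction with onset from the first fraction up to FU-2. Chronic: reactions present at, or arising after, FU-2. Say explicitly that a reaction with onset before FU-2 that is still present there enters both.
- At FU-1 and FU-2, have sites record the worst CTCAE grade since the previous visit, and amend 8.3.1, 8.3.2 and the schedule table accordingly.
- Align 8.3.2 with the scales named in 3.2.2. State whether the slash in 3.2.2 means both scales or either. If both are meant throughout, CTCAE recording is also needed at FU-3 to FU-6.

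Cost: edits to a few lines and one additional form at FU-2, a visit already scheduled (more forms only if both scales are kept to FU-6). The acute rate may come out less favourable because its window becomes longer. Sample size and the primary analysis do not change.

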5.1 Study Site Selection

The data collection is confined to radiooncological therapy centers with a high level of expertise in modern radiation treatment of GIL to ensure a consistent therapeutic standard and complete documentation.

Institutions would need to support the personnel completing the questionnaires.

5.2 Study Population

5.2.1 Inclusion Criteria

-primary indolent gastric or duodenal lymphoma

- pathology: marginal zone lymphoma (MZL) or follicular lymphoma (FL)
- stage: clinical stage I or II (Ann Arbor classification)
- H. pylori negative or antibiotic resistant lymphoma (defined as PD=progressive disease or NC=no change after antibiotic therapy; in case of NC the interval from H.p. eradication to RT is to be \geq 12 months)
- any FLIPI score low – high (0-4)
- any size of tumor or affected lymph nodes
- male or female with age \geq 18 years
- performance status ECOG 0 – 3
- written informed consent by the patient

5.2.2 Exclusion Criteria

- prior radiation treatment of the gastrointestinal lymphoma
- stage: clinical stage III or IV (Ann Arbor classification)
- inability to understand the informed consent or unwillingness to participate in the study
- severe comorbidity or organ dysfunction contraindicating the use of RT (liver cirrhosis Child-Pugh C, chronic obstructive pulmonary disease GOLD 4, heart insufficiency NYHA IV, dialysis dependent renal insufficiency, uncontrolled epilepsy)
- known seropositivity for HIV
- acute hepatitis B or C infection
- chronic inflammatory bowel disease
- prior malignant disease (exclusion: basalioma, non-metastasized solid tumor in constant remission diagnosed $>$ 3 years ago)
- pregnancy or breastfeeding
- active substance abuse or severely compromised compliance

6 Patient Inclusion, Registration

The announcement and dissemination of the study concept is to be executed via the medical organisations of radiooncologists, internal oncologists and gastroenterologists, and via the medical members of the International Lymphoma Radiation Oncology Group (ILROG).

Patients are recruited in the participating radiooncological centers (with expertise in radiation treatment of gastrointestinal lymphomas) after assignment by medical colleagues, as general practitioners, internists, gastroenterologists or internal oncologists. The therapeutic concept for a possible study patient can be specified in a multidisciplinary tumor conference or in interdisciplinary discussions with medical colleagues.

Patients who are cared for at one of the participating study sites and who are possibly eligible will be invited for study participation. Once written informed consent to participate in the study has been given (s. chapter 13.2), the patient will be assigned a subject identification code as follows: XX – YY (XX represents a unique number identifying the study site, YY is a continuously increasing number which is uniquely allocated to each patient recruited at the respective study site).

The maximum interval between enrollment in this study and initiation of radiation therapy must not exceed 3 months.

7 Investigational product/ Medical procedure

7.1 Radiotherapy for limited stage indolent lymphoma

7.1.1 Simulation/Planning-CT

The recommendations on planning are derived from the respective ILROG-guidelines for extranodal lymphomas (Yahalom 2015):

- planning and treatment should be performed with an empty stomach
- patient should be immobilized in a supine position with elevated arms
- a small amount (< 50 ml) of oral contrast agents should be administered, i.v. contrast agent is recommended in case of suspected lymph node involvement
- CT-scan should be performed before and after administration of oral contrast agent to account for stomach distension
- organ movement should be registered via 4D-CT-scan or fluoroscopy in order

to create an ITV

7.1.2 Target volume delineation

The target volume is delineated in a multi-step process according to the ILROG guidelines on ISRT and encompasses the involved gastric or intestinal region and includes the involved lymph nodes, depending on the stage of disease.

7.1.2.1 ISRT stomach

GTV: macroscopic tumor visible on PET, CT or both and pathological enlarged lymph nodes

CTV: GTV+ whole stomach from the esophagogastral junction to beyond the duodenal bulb. The whole wall of the stomach and perigastric lymph nodes, if visible, have to be included. In case of a duodenal wall infiltration, the whole duodenum has to be irradiated. In stage II, all further tumor manifestations are included in the CTV.

ITV: 4D-CT and fluoroscopy are used to account for gastric movements caused by breathing. In lack of these examinations, a margin of 1-2 cm is recommended.

PTV: dependent upon the setup variation, intraabdominal 1 cm around the final ITV is recommended

Organs at risk: kidneys (right/ left), liver, heart, lung (right/ left/ whole lung), small bowel, spinal cord

7.1.2.2 ISRT duodenum

CTV: If the lymphoma is confined to the duodenum, the whole duodenum is included in the RT field. In case of a possible involvement of the small bowel, a „whole abdomen“ technique is utilized to cover the intestine and mesentery. In stage II, all further tumor manifestations are included in the CTV.

7.1.3 Dosage and Technique

All dose specimen according to ICRU 83:

- Megavoltage photon irradiation should be use
- Dose prescription is 20 Gy, respectively in daily fractions of 2 G

- The use of modern techniques like intensity-modulated radiotherapy (IMRT) is encouraged (alternatively conformal RT with a 3D-plan may be used). Optional 4D-CT or PET-CT based planning
- For all RT plans, a dose volume histogram (DVH) for the target volume and neighbouring organs at risk (liver, kidneys, spinal cord, lungs, heart, small bowel) is compulsory
- verification: IGRT (image guided radiotherapy) with regular, daily is encouraged, conebeam- CT control.

7.1.4 Dose constraints

Dose constraints are defined according to **Quantitative Analysis of Normal Tissue Effects** in the **Clinic**:

- Kidneys $V_{20} < 32\%$, $V_{12} < 55\%$, mean dose < 18 Gy. In case of unilateral kidney or precedent functional impairment, lower doses may be necessary. In that case, a consultation with the reference radiation oncology is mandatory.
- Liver $V_{28} < 33\%$, mean dose < 20 Gy. In case of functional impairment (e.g. transaminase elevation, ascites), a consultation with the reference radiation oncology is mandatory.

In the eCRF the following dose parameters are to be documented:

- PTV: V95, V107, D98, D2, Dmean, Dmax
- Kidneys/ liver/ stomach/ duodenum/ small bowel: V10, V5, Dmean
- Heart/ lungs: V5, Dmean
- Body/ spinal cord: Dmax

8 Study conduct and study assessments

Visits	Trial							post-trial follow-up		
	BV	IV-1	IV-2	IV-3	IV-4	FU-1	FU-2 + FU-3	FU-4	FU-5	FU-6 (Final examination)
	Baseline visit	First day of RT	Second day of RT (after 4 Gy)	5th day of RT (after 10 Gy)	Last day of RT (after 20 Gy)	6 weeks after end of RT ± 5 d	3 and 6 months after end of RT ± 3 weeks	9 months after end of RT ± 3 weeks	1 year after end of RT ± 3 weeks	2 years after end of RT ± 3 weeks
Informed Consent	X									
Inclusion / Exclusion Criteria	X									
Registration	X									
Medical history, concomitant diseases	X									
Concomitant medication	X									
Demographic data	X									
Anamnesis	X	X	X	X	X	X	XX	X	X	X
Clinical Examination	X	X	X	X	X	X	XX	X	X	X
Endoscopy/ Endosonogra	X X						XX XX		X X	X X

phy (+ biopsies)											
CT-imaging (Routine Staging and follow-up care)	X (+Routine Planning-CT)						only at 6 months		X	X	
PET-CT (optional)	(X)						(X)				
Abdominal ultrasound	X										
Quality of life assessment	X				X		only at 6 months				
Blood draw	X		X	X	X		XX				
Radiation treatment		20 Gy (two weeks)									
Adverse acute reactions		X	X	X	X	X					
Adverse chronic reactions							XX	X	X	X	
Adverse events		X									
Final examination										X	

IV=intermediate visit, FU=follow-up

